### **6.2.5 Physical Examinations**

Physical examinations will be performed in accordance with the Schedule of Procedures (Table 5).

A physical examination covering the major body systems (general appearance, head [ear, nose and throat], cardiovascular, eyes, respiratory, abdomen, urogenital, musculoskeletal, neurological, lymph nodes and skin) will be performed at screening (baseline), last day at ICU and at D28 (or when patient withdraws from the study prior to D28).

At screening the physical examination will also include:

- Predicted body weight (PBW). Calculate the PBW (kg) using the following formulae:  
For men:  $50 + 0.91(\text{height in cm} - 152.4)$   
For women:  $45.5 + 0.91(\text{height in cm} - 152.4)$
- Actual height (in cm). The patient's height does not need to be measured immediately if recorded elsewhere in the medical records or provided 'anecdotally' by relatives (the PBW can then be calculated as described above).

## **6.3 Demographics and Baseline Characteristics**

Demographics and baseline characteristics consist of those variables that are assessed only at screening/baseline.

### **6.3.1 Patient Demography**

Patient demography consists of:

- Age at screening
- Race
- Sex

### **6.3.2 Disease History**

For disease history, the following will be documented:

- Time and date of moderate or severe ARDS diagnosis
- Underlying aetiology of moderate or severe ARDS
- Chest X-ray or CT scan
- PaO2/FiO2 ratio element of moderate or severe ARDS diagnosis along with associated PEEP

The chest X-ray or CT scan and the confirmatory assessment of PaO2/FiO2 ratio along with associated PEEP must occur within the same 24-hour period.

### **6.3.3 Medical History**

For documentation of the medical history, any relevant previous and ongoing medical conditions with a start date before the time of informed consent should be documented. Conditions that resolved long before informed consent and have no impact on the disease being studied should not be listed.

The medical history should be obtained by inspecting the patient's medical records or by interviewing the patient or their relatives.

**Table 4 APACHE II score**

VARIABLE	Recorded value	Points scored	POINT VALUE RANGE								
			+4	+3	+2	+1	+0	+1	+2	+3	+4
Core temperature (°C)		≥41	39.0-40.9		38.5-38.9	36.0-38.4	34.0-35.9		32.0-33.9	30.0-31.9	≤29.9
Mean arterial pressure (mmHg)		≥160	130-159	110-129		70-109			50-69		≤49
Heart rate (beats/min)		≥180	140-179	110-139		70-109			55-69	40-54	≤39
Respiratory rate (breaths/min)		≥50	35-49		25-34	12-24	10-11		6-9		≤5
If FIO 2 ≥ 0.5 use A-aDO 2 (kPa)		>67	47-66	27-46		<27					
If FIO 2 < 0.5 use PaO 2 (mmHg)		≥500	350-499	200-349		<200					
If FIO 2 < 0.5 use PaO 2 (kPa)						>9.3	8.1-9.2	61-70		7.3-8.0	<7.2
Arterial pH		≥7.7	7.6-7.69		7.5-7.59	7.33-7.49			7.25-7.32	7.15-7.24	<7.15
If no ABG use HCO 3 (mmol/L)		≥52	41-51.9		32-40.9	22-31.9			18-21.9	15-17.9	<15
Sodium (mmol/L)		≥180	160-179	155-159	150-154	130-149			120-129	110-119	≤110
Potassium (mmol/L)		≥7	6-6.9		5.5-5.9	3.5-5.4	3-3.4		2.5-2.9		<2.5
Creatinine (µmol/L)*		>309	309-177	176-133		132-53			<53		
Haematocrit (%)		≥60		50-59.9	46-49.9	30-45.9			20-29.9		<20
White blood count (10  /L)		≥40		20-39.9	15-19.9	3-14.9			1-2.9		<1
Clinical & laboratory points											

\* If the patient has acute renal failure then the score for serum creatinine will be doubled

NEUROLOGICAL POINTS (15 minus the GCS)		AGE POINTS		CHRONIC HEALTH POINTS		
Eye opening 4 – spontaneously 3 – to verbal 2 – to painful stimuli 1 – no response  Motor response 6 – to verbal command 5 – localizes to pain 4 – withdraw to pain 3 – flexion abnormal 2 – extension abnormal 1 – no response	Verbal response - not intubated 5 – oriented and converses 4 – disoriented and talks 3 – inappropriate words 2 – incomprehensible sounds 1 – no response  Verbal response - tracheal tube 5 – seems able to talk 3 – questionable ability to talk 1 - generally unresponsive  For patients who are sedated use an estimated score for GCS (the assumption is 15, if no other factors than sedation affect GCS)	≤44 45 – 54 55 – 64 65 – 74 ≥75	0 2 3 5 6	Does patient have any of the following? Liver – Cirrhosis with PHT or encephalopathy Cardiovascular – NYHA IV Respiratory – Chronic obstructive or vascular disease resulting in restriction or chronic hypoxemia, hypercapnia or polycythaemia, severe pulmonary hypertension >400 mmHg Renal – Chronic CAPD or HD Immune – Immunocompromised host  If any box above is checked YES then: a. Medical or emergency postop - assign 5 points b. Elective postop - assign 2 points	Yes	No
		Neurological points =  Clinical & laboratory points =				
A	Acute Physiology Points	B	Age Points	C	Chronic Health Points	Add A + B + C APACHE II score

#### **6.3.4 Previous and Concomitant Medications**

Previous (in the month before screening) and concomitant medications will be documented as described in Section 5.7.

#### **6.4 Pharmacoeconomic Evaluation**

Variables that will be measured as part of cost-effectiveness at D28 are:

- Days free of organ failure (SOFA methodology) (D28 or last day in ICU if patient has left the ICU earlier than D28, or at withdrawal)
- Days free of renal support
- Days free of vasoactive support
- Days free of mechanical ventilation
- Number of ICU-free days
- Number of days in hospital

#### **6.5 Exploratory Variables**

##### **6.5.1 Improvement in Gas Exchange**

The gas exchange ( $\text{PaO}_2/\text{FiO}_2$  ratio) of patients on mechanical ventilation will be evaluated. The  $\text{PaO}_2/\text{FiO}_2$  ratio will be used as an indicator of lung function.

##### **6.5.2 Biomarkers: CD73 and Potential Inflammatory Markers (PIM)**

Blood samples for the CD73 and PIM assessments will be collected pre-dose on D1 (baseline) and daily from D2 to D14 as detailed in the Schedule of Procedures (Section 7.1, Table 5). Fourteen samples of 2.5 mL will be collected for CD73 and PIM; from these, samples will be prepared for the CD73 and PIM testing. CD73 and PIM blood sample preparation and sample storage details are provided in the Laboratory Manual. It is essential that the actual time and date of collection of each sample is recorded in the sample collection form provided with the laboratory kits. CD73 samples will be analysed centrally by Wieslab AB; PIM samples will be analysed at MediCity Research Laboratory, University of Turku, Turku, Finland.

##### **6.5.3 Pharmacogenetics**

The genetic sample can be taken at any time that the patient is in the ICU if consent has been obtained. The objectives of the genetic sampling are to obtain blood for extraction of DNA to identify factors that may be involved in the response or non-response of diseases to FP-1201-lyo and comparator compounds.

The blood sample will be taken for extraction of DNA. This is optional for all patients entering the study and will involve a separate patient consent procedure. Consenting to genetic sampling is not a prerequisite to participating in the main study.

A 10 mL blood sample will be collected; sample preparation and sample storage details are provided in the Laboratory Manual.

The samples and data for genetic analysis in this study will be coded. Samples will not carry any personal identifiers. DNA samples will be destroyed 15 years after

completion of this study. If the patient withdraws the consent, the sample will be destroyed without undue delay.

## 7 STUDY CONDUCT

For the purposes of this study, study day 1 (D1) is defined as the first calendar day (from midnight to the following midnight) of treatment with FP-1201-lyo or placebo. All days thereafter are defined as “Dn” (e.g., D2, D3, etc.) until D28. After D28 the study assessments are performed on D90 (3 months; either a clinic visit or telephone contact), D180 (6 months) and D360 (12 months).

Baseline assessments are defined as those assessments carried out in the screening period and before the first dose of study drug on D1. It is critical that the time from diagnosis of moderate or severe ARDS to administration of the first dose of FP-1201-lyo or placebo is less than 48 hours.

Unless withdrawn from study, all patients will receive study drug for 6 days.

All assessments in the period up to D28 are only to be performed when a patient is in the ICU. If an improving patient is discharged from the ICU during the short-term follow-up period then the assessments under ‘last day in the ICU’ will be carried out and the survival status and other endpoints must be assessed on D28.

There are three follow-up periods:

- Short term: D7 to D28
- Long term: D90 [3 months] and D180 [6 months]
- Extended: D360 [12 months] (last visit)

The end of the study will be the date of last patient/last visit at D360.

### 7.1 Schedule of Procedures

**Table 5 Schedule of Procedures**

Procedure	Screening period	Double-blind treatment period Days 1-6		Short-term follow-up until D28 or discharge from ICU (whichever is earlier)					Long-term follow-up		Extended follow-up
	48 h a	D1 pre-dose	D1	D2-D6	D7-D14	D15-D27	Last day in ICU b	D28 c	D90 d +14 days	D180 +14 days	D360 +14 days
Informed consent	X		Administration of study drug								
Medical history	X										
Demographic details	X										
Documentation of chest X-ray or CT scan	X										
Inclusion/exclusion criteria	X	X e									
Randomisation		X f									
Administration of study drug			X	X							
Survival				X							X
On mechanical ventilation? (Y/N)				X							X
In ICU/in hospital? (Y/N)				X							X
SOFA		X		X	X	D21	X	X o			
GCS (for SOFA and APACHE II)	X	X		X	X	D21	X	X o			
APACHE II	X b										
Renal and vasoactive support? (Y/N)		X		X				X			

Procedure	Screening period		Double-blind treatment period Days 1-6				Short-term follow-up until D28 or discharge from ICU (whichever is earlier)				Long-term follow-up			Extended follow-up
	48 h a	D1 pre-dose	D1	D2-D6	D7-D14	D15-D27	Last day in ICU b	D28 c	D90 d +14 days	D180 +14 days	D360 +14 days			
Blood sample: IFN beta-1a neutralising antibodies		X h						X	X					
Blood sample: MxA		X h		X	X									
EQ-5D-3L, FEV 1 and GMWT										X		X		
PaO 2 /F i O 2	X	X		X	X	X	X	X						
Blood sample: CD73 and PIM		X h		X	X									
Pharmacoeconomics														
Physical examination	X						X	X						
Vital signs	X i	X	Administration of study drug				X	X	X					
ECG		X			D7					X		X		
Haematology, chemistry, urinalysis k	X i	X		X	X	X	X	X		X o				
Pregnancy test in women of childbearing potential	X													
Previous and concomitant medications and therapies	X l	X												
Adverse events	X m	X							X	X n	X n	X n		
Blood sample: genetic analysis (requires separate consent)	X													

a No more than 48 hours may elapse between confirmation of moderate or severe ARDS and administration of the first dose of study drug.

b These assessments will be done on the day the patient leaves the ICU, which will either be on D28 or earlier, according to the clinical progress of the patient. If the patient is still in the ICU on D28, the next visit or telephone contact will be at D90. If a patient leaves the ICU before D28, the survival status and other endpoints must be assessed on D28.

c D28 procedures apply for patients leaving the ICU before D28 and for patients withdrawing from the study before D28. For patients withdrawing from the study before D28 a sample should be taken for neutralising antibodies on the day they leave the ICU.

d D90 can either be a visit or telephone contact.

e Reconfirm inclusion/exclusion criteria before dosing, including that patient requires mechanical ventilation and is in the ICU (patients requiring ECMO after randomisation but before the first dose of IMP may still be included).

f Randomise after consent obtained and once eligibility criteria confirmed.

g Within 24 hours of ICU admission

h Within 1 hour pre-dose.

i Baseline EQ-5D-3L to be obtained from relatives and checked later with patient.

j For APACHE II scoring.

k Samples should be taken in the morning between 04:00 and 10:00.

l Medicines and therapies in previous month.

m Adverse events will be recorded after informed consent is obtained.

n Deaths are reported as SAE

o if it is possible to be performed by the investigator

Abbreviations: APACHE II=Acute Physiology and Chronic Health Evaluation; CD=cluster of differentiation; CT=computerised tomography; D=study day; ECG=electrocardiogram; ECMO=extra-corporeal membrane oxygenation; EQ-5D-3L=EuroQol 5-Dimensions 3-Levels questionnaire; FEV1=forced expiratory volume in 1 second; GCS=Glasgow Coma Scale; ICU=intensive care unit; IFN=interferon; MxA=myxovirus resistance protein A; PaO2/FiO2=partial pressure of oxygen/fraction of inspired oxygen; PIM=potential inflammatory marker; SOFA=Sequential Organ Failure Assessment; 6MWT=6-minute walk test.

## 7.2 Procedures by Visit

All times should be recorded using 24-hour clock (i.e., 23:20 not 11:20 pm). Where a patient's condition precludes an assessment taking place as scheduled, the assessment should be performed within  $\pm 4$  hours of the scheduled time; if this is not possible, the assessment will not be performed and the reason for non-performance should be recorded.

### 7.2.1 Pre-screening Evaluation and Screening Log

A complete screening and pre-first-dose evaluation will be conducted including the procedures outlined in Sections 7.2.2.1 and 7.2.2.2 below.

Patients will be considered for entry into the study when a diagnosis of moderate or severe ARDS has been made. Before being randomised, patients will be assessed to ensure that all eligibility criteria are met. Patients not meeting the eligibility criteria must not be randomised. Faron Pharmaceuticals Ltd will not permit any exceptions to the eligibility criteria and protocol waivers will not be given.

When considering patients for the study, the investigational site will review:

- The criteria for moderate or severe ARDS diagnosis to verify that all elements are present (refer to Inclusion Criterion 1 as per Section 4.1)
- The time of moderate or severe ARDS diagnosis to ensure the 48-hour study treatment window is still available (refer to Inclusion Criterion 3 as per Section 4.1)
- All eligibility criteria (refer to Sections 4.1 and 4.2)
- Provision of informed consent. Study-specific procedures must be performed after informed consent for the study is given. **Note:** When the **ICU normal procedures** of patients **are in line with the study procedures**, and if the timing of moderate or severe ARDS diagnosis, consent and dosing preclude repeat of procedures for the purposes of the study, then normal patient care test results may be used for screening even if **prior** to consent.

Investigational sites will review all ICU patients daily in order to identify potential patients for this study. Only patients that are intubated and mechanically ventilated are eligible for the study. Investigational sites will maintain a log for all patients that fulfil the intubation, mechanical ventilation and hypoxaemia ( $PEEP \geq 5$  cmH2O and  $PaO_2/FiO_2 \leq 200$  mmHg) inclusion criteria. For patients meeting these criteria the other criteria for ARDS diagnosis according to Berlin definition (Ref: ARDS Definition Task Force 2012) as well as the other study inclusion and exclusion criteria shall be reviewed and documented on the log, whether or not the patient is entered into the study.

The log will be sent to the CRO on a weekly basis while the investigational site is open for recruitment.

### 7.2.2 Screening Assessments and Pre-dose Procedures

#### 7.2.2.1 Screening Assessments to Be Performed After Moderate or Severe ARDS Diagnosis and Within 48 hours Prior to the First Dose of Study Drug

Screening assessments will be carried out after informed consent and must be completed before the first dose of study drug is administered. **The first dose of study drug must be administered within 48 hours of moderate or severe ARDS being diagnosed.**

The following parameters will be reviewed and the data will be recorded in the e-CRF once the patient has given informed consent (refer to Schedule of Procedures in Table 5):

- Date and time of informed consent
- Allocated patient screening number
- Moderate or severe ARDS disease history including:
  - Time and date of moderate or severe ARDS diagnosis
  - Underlying aetiology of moderate or severe ARDS
  - Documentation of chest X-ray or CT scan
  - PaO2/FiO2 ratio element of moderate or severe ARDS diagnosis along with associated PEEP
- Medical history including any concomitant diseases within the last 1 month before screening
- Date and time of entry to ICU
- Date and time of intubation and mechanical ventilation
- Review of the inclusion and exclusion criteria
- Demographic data including age at screening, race and sex
- Physical examination of major body systems including PBW (refer to Section 6.2.4 for the calculation formula) and height
- Pregnancy test: All women of childbearing potential must have a pregnancy test. The patient will be considered to lack childbearing potential if surgically sterile (e.g., hysterectomy, bilateral oophorectomy) or postmenopausal (amenorrhoea >12 months). A urine pregnancy test will be performed; if the patient is not producing urine a serum pregnancy test will be performed instead
- APACHE II score; this is based on the worst values in the first 24 hours following admission to the ICU of the following 12 variables (see Table 4) but before the first dose
  - A-aDO2 or PaO2 (depending on FiO2)
  - Temperature (rectal or other core site)
  - Mean arterial pressure
  - Arterial pH
  - Heart rate
  - Respiratory rate
  - Sodium
  - Potassium
  - Creatinine
  - Haematocrit
  - White blood cell count
  - Glasgow Coma Scale
- Genetic sample obtained if consent has been given (refer to Section 6.5.3). The genetic sample can be taken at any time while the patient is in the ICU if consent has been obtained

- Randomisation to a study treatment group may occur when all the inclusion/exclusion criteria are met and must follow the pre-dose eligibility check as described in Figure 2. The randomisation number along with the date and time of randomisation will be recorded
- AEs
- Previous and concomitant medications and therapies

#### 7.2.2.2 *Pre-dose Procedures to Be Performed on D1 Before the First Dose of Study Drug is Administered*

**Note:** Prior to the first administration of any study drug on D1, the patient's moderate or severe ARDS status (as per Inclusion Criterion 1 in Section 4.1) must be confirmed. That the patient continues to be on mechanical ventilation must also be confirmed. If both criteria are not confirmed, the patient should be withdrawn from the study and will be classed as a screen failure.

On D1 all pre-dose procedures and assessments are to be performed **before the first dose of study drug**.

The following procedures and assessments will be performed:

- Review of the inclusion and exclusion criteria to ensure continued eligibility, including a check that the patient is in the ICU and on ventilation
- Check PaO2/FiO2 ratio
- Randomisation: randomisation number and date and time of randomisation will be recorded
- SOFA scoring will be done pre-dose based on the worst value so far that day for each of the following parameters:
  - PaO2/FiO2 (mmHg)
  - platelets × 10^3/mm^3
  - bilirubin (µmol/L or mg/dL)
  - hypotension/use of vasopressors
  - GCS
  - creatinine (µmol/L or mg/dL) or urine output
- APACHE II scoring will be done on the worst values in the 24 hours following ICU admission or up to the time of the first dose if the patient has been on the ICU less than 24 hours (see Table 4).
- The following ventilation variables should be recorded in the morning between 04:00 to 10:00 using the values closest to 10:00 (if these values are representative of the patient's condition), whenever possible:
  - Mode of ventilation (whether predominantly volume or pressure set)
  - Tidal volume (ml)
  - Respiratory rate (breaths per min) - total respiratory rate will be used if the patient is breathing spontaneously on a mechanical ventilator
  - Peak inspiratory pressure (cmH2O)
  - Plateau pressure (cmH2O) - if set
  - Mean airway pressure (cmH2O)
  - PEEP

- All ventilator assessments must be taken at the same time point whenever possible and should be representative of the values over the recent past. PEEP is not available if using HFOV.
- Recording of vasoactive drugs and renal support
- Perform ECG
- Vital signs (respiratory rate, temperature, blood pressure [BP] and HR) must be measured and recorded in the morning between 04:00 and 10:00 using the values closest to 10:00 (if these values are representative of the patient's condition). All vital sign assessments must be taken at the same time point whenever possible
- Blood biochemistry: samples must be taken in the morning between 04:00 and 10:00 using the values closest to 10:00 (refer to Section 6.2.2 for specific biochemistry variables)
- Haematology: samples must be taken in the morning between 04:00 and 10:00 using the values closest to 10:00 (refer to Section 6.2.2 for specific haematology variables)
- Urinalysis (if the patient is producing urine): samples for the urinalysis dipstick must be taken in the morning between 04:00 and 10:00 using the values closest to 10:00 (refer to Section 6.2.2 for specific urinalysis variables)
- Neutralising antibody sample for central testing (refer to Section 6.1.2.4)
- MxA sample for central testing taken within 1 hour pre-dose (refer to Section 6.1.2.5)
- CD73 and PIM biomarker samples for central testing taken within 1 hour pre-dose (refer to Section 6.5.2)
- Obtain baseline EQ-5D-3L from relatives
- Recording of concomitant medications and therapies
- Recording AEs

### **7.2.3 Treatment Period: D1 Dosing and Post-dose**

- Day 1: The first dose of study drug (FP-1201-lyo or placebo) will be administered as an intravenous bolus injection (see Section 5.2).
- Record SOFA scores. **Note:** The worst daily value of each element should be used to calculate the overall SOFA score
- Recording of concomitant medications and therapies
- Recording of AEs

### **7.2.4 Treatment Period: D2 to D6**

Assessments from D2 to D6 are only performed when a patient is in the ICU. The following assessments are to be done daily:

- Check patient survival
- Confirm patient is in the ICU
- Check whether the patient is on ventilation (refer to Section 6.1.1 for definition of UAB)
- Administer the study drug (FP-1201-lyo or placebo) as an intravenous bolus injection **24 hours ±1 hour after the previous day's administration.** If for any

reason this is not possible, the dosing window may be extended by **up to 4 hours**. The reason for the delay must be entered in the e-CRF (see Section 5.2) Subsequent doses should not be delayed and should revert to the original time schedule.

- Record SOFA scores
- Recording of vasoactive drugs and renal support
- Vital signs (temperature, BP and HR) must be measured and recorded in the morning between 04:00 and 10:00 using the values closest to 10:00 (if these values are representative of the patient's condition). All vital sign assessments must be taken at the same time point whenever possible.
- Haematology, biochemistry and urinalysis: samples must be taken daily in the morning between 04:00 and 10:00 using the values closest to 10:00
- MxA, CD73 and PIM samples for central testing are taken within 22 hours  $\pm 2$  hours after the previous day's administration of study drug, however before the next study drug dose.
- Recording of concomitant medications and therapies
- Recording of AEs

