The no observed adverse-effect level (NOAEL) for IFN beta-1a in cynomolgus monkeys was considered 3.0 MIU/kg/d for 28 days. In a 70 kg human this would translate to a dose of 210 MIU/d or a total dose of 1260 MIU over 6 days. The proposed daily dose for this clinical study is 2.7 MIU/d (10 µg/d), i.e., a total of 16.2 MIU (60 µg) over 6 days. The NOAEL is therefore 77.7 times the proposed 6-day exposure to IFN beta-1a.

Recombinant human IFN beta-1a (FP-1201) was assessed for the treatment of ALI and ARDS (1994 American-European Consensus Conference definition of ALI/ARDS (Ref: Bernard et al 1994)) in a Phase I/II study (FPCLI001) (Ref: Bellingan et al 2014). This open-label study included 37 patients with ALI/ARDS and the optimum tolerated dose (OTD) was shown to be FP-1201 10 µg daily for 6 days. The primary efficacy endpoint was the Day 28 mortality rate, which was 8.1% in the safety population – well below that normally seen in ICUs in the UK for patients with ALI/ARDS. From the literature, Day 28 mortality rates for ALI/ARDS vary from

20% (ALI) to over 60% (ARDS), with a generally accepted figure of approximately 40%.(Ref: Phua et al 2009, Doyle et al 1995, Zilberberg et al 1998, Sloane et al 1992) The long-term efficacy endpoint of 6-month mortality also demonstrated a mortality rate well below that expected for this population of patients. Four of the 37 patients died before the 6-month time point.

Pyrexia was the most common drug-related treatment-emergent adverse event (TEAE) in the study. All pyrexia events resolved rapidly without sequelae. Clinically significant low haemoglobin values were recorded in all cohorts at different time points during the study (including both at screening and at Day 28). No other trends in laboratory values or other safety variables were observed from baseline to Day 28. Data from the measurements of vital signs, electrocardiograms (ECGs), other laboratory data (biochemistry and haematology) and physical examinations showed no clear trends. At Day 28, chest X-rays for 19 patients showed improvements since the previous assessment.

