### 1.3 Risk/Benefit Assessment

Non-clinical data reveal no special hazard for humans treated with FP-1201 in conventional studies of safety, pharmacology, repeated-dose toxicity and genotoxicity.

ARDS is a severe condition with a high mortality rate, despite progress in ICU medicine. Currently there is no approved pharmacological therapy available for ARDS. Patients with ARDS are treated with intensive support, which includes various strategies for assisted ventilation. The results of the Phase I/II study (FPCLI001) provided evidence for the beneficial effect of FP-1201 in patients with ARDS and fully supported the conduct of a pivotal and well-controlled Phase III study.

IFNs were the first cytokines to be administered to humans; they are endogenous pyrogens and fever has been recognised as a frequent event. The febrile response varies with the dose, type and route of administration. Fever is characterised by preceding mild malaise and shaking chills that lead to elevation of body temperature. IFNs only occasionally cause rigors, in contrast to tumour necrosis factors. There is a well-described thermal ceiling, which means that fever does not exceed certain levels, regardless of the dose of IFN used. In addition, pyrogenic tolerance often develops with daily administration. This gradual diminution in pyrogenicity is one of the hallmarks of IFN therapy, a characteristic not shared by therapy with other pyrogenic cytokines.

On the first day of IFN therapy, the patient's temperature characteristically reaches 38–39°C (orally) 5–6 hours after IFN administration, and this elevation persists for around 2 hours. The temperature elevations experienced by patients vary substantially between individuals. The pyrogenic effect (high fever, rigors and chills) of IFN beta-1a was observed in the Phase I/II study at the highest dose of FP-1201 22 µg; this was shown to be the maximum tolerated dose.

IFN-induced fever responds to antipyretic analgesic drugs and they are recommended to decrease or prevent the flu-like symptoms associated with FP-1201-lyo administration.

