### 5.2 Administration

FP-1201-lyo 10 µg (or placebo) will be diluted in WFI near the patient/in the ICU. Once prepared, the dose must be administered to the patient immediately. The diluted FP-1201-lyo or placebo will be administered as an intravenous bolus injection via a central or peripheral line. The injection will be followed with a 5 mL flush of sterile saline (not provided).

FP-1201-lyo and placebo injections will be given once daily for 6 days. The injection should be given at the same time each day  $\pm 1$  hour providing the patient's condition allows this. If for any reason this is not possible, the treatment window may be extended by up to 4 hours. The reason for the delay must be entered in the e-CRF. Subsequent doses should not be delayed and should revert to the original time schedule (e.g., if the D1 dose was at 13:00, the D2 dose was delayed and given at 17:00, the D3 dose should be given at 13:00  $\pm 1$  hour).

No dose modifications or temporary cessations of study drug administration are allowed. If a delay beyond the 4-hour window described above is required, the patient must be withdrawn from study drug but all data must continue to be collected per protocol. Administration of a second course of study drug is not permitted.

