### **6.2.3 Vital Signs**

Vital signs will be measured supine pre-dose on D1 (baseline) and daily up to D28 while the patient is in the ICU, as detailed in the Schedule of Procedures (Section 7.1, Table 5). The date and time of collection of each parameter will be recorded in the e-CRF.

Vital sign variables are:

- Blood pressure (systolic, diastolic and mean; mmHg): to be recorded via an arterial line
- Heart rate (HR; bpm): measured as per clinical practice in each ICU
- Total respiratory rate (breaths per minute)
- Temperature (°C): core temperature to be measured according to the site's usual practices and the site of measurement should be recorded in the e-CRF

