### **8.6.2 Vital Signs**

Vital signs data (BP, HR and temperature) will be summarised using descriptive statistics (mean, median, SD, minimum and maximum) by treatment group separately at D1 and daily to D28. The maximum change from baseline over the 28-day follow-up period will be calculated for each patient and summarised.

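### Scheduled temperature readings follow the clock and not the dose, so the by-arm temperature summaries are poorly placed to show the fever the protocol expects about 5–8 hours after dosing

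*Protocol*

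**What the plan says.** **What fever is expected.** Protocol 1.3 says that on the first day of interferon therapy the patient's "temperature characteristically reaches 38–39°C (orally) 5–6 hours after IFN administration, and this elevation persists for around 2 hours". It adds that individuals vary substantially, that tolerance often develops with daily dosing, and that antipyretics are recommended. On the earlier Phase I/II study, Protocol 1.1.2 reports: "Pyrexia was the most common drug-related treatment-emergent adverse event (TEAE) in the study".

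**When temperature is recorded.** Protocol 6.2.3 gives the schedule: "Vital signs will be measured supine pre-dose on D1 (baseline) and daily up to D28 while the patient is in the ICU". The D1 list in Protocol 7.2.3 opens with "The first dose of study drug (FP-1201-lyo or placebo) will be administered as an intravenous bolus injection" and then has SOFA, concomitant medications and adverse events. It has no vital signs. For D2–D6, Protocol 7.2.4 says: "Vital signs (temperature, BP and HR) must be measured and recorded in the morning between 04:00 and 10:00 using the values closest to 10:00", with the qualifier "if these values are representative of the patient's condition". SAP 5.8.1 repeats the schedule and adds no post-dose reading on D1.

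**When the drug is given.** The clock time of dosing is not fixed. It is set by the first dose, and later doses follow at 24-hour intervals with a tolerance. Protocol 5.2 gives an example: "if the D1 dose was at 13:00".

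**What is summarised.** Protocol 8.6.2 plans daily summaries and also: "The maximum change from baseline over the 28-day follow-up period will be calculated for each patient and summarised". SAP 7.3.2 lists values and changes from baseline at each assessment and at the last observation. It does not mention the maximum change. Extra vital signs taken outside the schedule are listed but not summarised (Protocol 8.2.1.3, SAP 5.9.2).

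**The concern.** The protocol names one acute drug effect with a known time course, and then schedules the relevant measurement without reference to the dose. The same section that sets the morning reading does tie the MxA, CD73 and inflammatory marker samples to the previous day's dose (22 ± 2 hours), so dose-linked timing was considered practicable for other measurements.

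At stake is how the temperature tables will be read. If the readings fall outside the hours when fever is expected, the two arms can look alike in those tables whether or not the drug raises temperature, and a reader could take that as reassurance. The maximum change in Protocol 8.6.2 does not help, because it is a maximum over the same morning readings.

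**Working it through.** The plan states no figure on this point, so there is nothing to reproduce. The check is one of clock times.

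**Inputs**
- Fever window: onset 5–6 h after dosing, lasting about 2 h (Protocol 1.3). Earliest start is 5 h and latest end is 6 + 2 = 8 h, so the window is 5–8 h post-dose.
- Reading time: 04:00–10:00, value closest to 10:00 (Protocol 7.2.4).
- D1: pre-dose reading only (Protocol 6.2.3 and 7.2.3, SAP 5.8.1).
- Dose time T, in hours after midnight: not fixed, so varied over 0–24.

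**Formula.** Lag = reading time − dose time. The reading catches the window if the lag is between 5 and 8 h.

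**First dose, next scheduled reading on D2**
- Reading at 10:00: lag = 34 − T. As T runs from 0 to 24, the lag runs from 34 down to 10 h. It is never 8 h or less, so no dose time is caught.
- Reading at 08:00: lag = 32 − T, always above 8 h. None caught.
- Reading at 06:00: lag = 30 − T, caught for doses at 22:00–24:00.
- Reading at 04:00: lag = 28 − T, caught for doses at 20:00–23:00.

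The first-dose fever could therefore be seen only if a late-evening dose were followed by a recorded value from early in the morning window. The instruction to take the value closest to 10:00 works against that.

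**Doses 2–6, reading at 10:00**
- Lag since the most recent dose = (10 − T) modulo 24.
- 5 ≤ lag ≤ 8 gives T between 02:00 and 05:00.
- Share of clock times: 3/24 = 12.5%, if dose times were uniform over the day.
- For doses between 10:00 and midnight the next 10:00 reading comes at least 10 h later, so none are caught.

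**Protocol example, dose at 13:00**
- Window: 13:00 + 5 h = 18:00 to 13:00 + 8 h = 21:00.
- Next reading: 15 h post-dose if taken at 04:00, 21 h if taken at 10:00. Missed either way.

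Uniform dose times are an assumption. Protocol 7.2.2.2 asks for the D1 pre-dose vital signs and blood samples in the same 04:00–10:00 slot. That suggests many first doses would follow the morning set, with later doses about 24 h apart. If so, the share caught would be below 12.5%. The documents give no distribution of dose times.

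**The case against.** The strongest reply is that fever has another route into the results. Adverse events are recorded after the D1 dose and daily afterwards. Protocol 6.2.1.2 requires documentation whatever the source. Protocol 6.2.1.3.4 covers abnormal vital signs expressly. SAP 7.3.1 tabulates treatment-emergent events by arm, with relatedness and intensity, and the IDMC reviews adverse events unblinded. In the earlier study pyrexia did emerge as an adverse event even though, according to Protocol 1.1.2, vital signs showed no clear trends. A fixed morning slot, shared with the laboratory and ventilation variables, is also a reasonable standardisation.

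Most of this stands. A reader might infer that the safety objective goes unanswered for fever. The documents do not support that, because adverse event reporting remains open. It is filtered, though: Protocol 6.2.1.3 says common ICU abnormalities need not count unless they require significant intervention, lead to stopping the drug or concern the investigator, and Protocol 6.2.1.3.4 leaves out findings associated with the disease unless they are worse than expected. The earlier study was also open label. Its result shows that a pyrexia signal can coexist with uninformative vital sign data, which is the situation described here.

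Three further inferences should be resisted.
- **No temperature after the first dose.** True only for the rest of D1; daily readings resume on D2.
- **A diluted effect in °C.** The 12.5% is a share of clock times under an assumption. It cannot be used to scale a temperature rise, because the rise at this dose, its variation, tolerance and antipyretic use are not quantified. Protocol 1.3 reports high fever for the earlier study at 22 µg, whereas this trial uses 10 µg.
- **Masked heart rate or blood pressure effects.** Protocol 1.3 describes no such effect, and SOFA already takes the worst daily cardiovascular value.

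**Conclusion.** The point holds for measured temperature and its by-arm summaries. No scheduled reading is tied to the dose. A 10:00 reading on D2 misses the first-dose window for every possible D1 dose time, and this is the day for which the protocol describes the fever. For doses 2–6 a 10:00 reading catches it only for doses at about 02:00–05:00.

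This rests on the 5–8 h window from Protocol 1.3, on the recorded value being close to 10:00 and, for the 12.5% only, on uniform dose times. The representativeness qualifier and the 04:00–10:00 range allow some exceptions, but neither links a reading to a dose. How much temperature signal is lost cannot be computed from the documents. These are descriptive safety tables without formal testing, so this is a cheap improvement and not a threat to the trial's main conclusions.

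**What to change.** - **e-CRF, D1–D6:** record the highest charted core temperature in the 24 h after each dose (at minimum the first 8 h), starting with the first dose. Keep the morning value as the routine reading.
- **SAP 7.3.2:** tabulate by arm the maximum temperature and the maximum change from pre-dose baseline, for each dosing day and overall. This also restores the maximum-change summary that Protocol 8.6.2 promises and the SAP omits. A maximum of several readings will tend to exceed a single baseline value in both arms, so the table should be read as a comparison between arms.
- **If the e-CRF can no longer be changed:** restore the maximum-change summary, and state beside the temperature tables that readings were not timed to the dose and that pyrexia rests on adverse event reporting.

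Cost: one field per dosing day, so six per patient, and one table. This assumes that ICU charts already hold the values, which the documents do not state. No change to treatment or to patient procedures is needed.
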